9.4.3.3. Secondary analyses

In case analysis of the primary endpoints leads to rejection of null hypotheses, the following key secondary endpoints will be tested in a conditional sequential manner to show superiority of cenegeerin versus control (at alpha one-sided 0.025) according to the following ranking:

1. Change from baseline in Schirmer I test (without anesthesia) at week 8;
2. Change from baseline in SANDE scores for severity at week 12;
3. Change from baseline in SANDE scores for frequency at week 12;
4. IDEEL modules (Quality of Life [27 questions], Dry eye Treatment satisfaction & Bother [10 questions], and Dry eye Symptom bother [20 questions]) at week 12 and at week 4 (in this order);
5. Change from baseline in Cornea and conjunctiva vital staining with fluorescein NEI scales at week 4, week 8 and at week 12 (in this order);
6. Change from baseline in TFBUT at week 4, week 8 and at week 12 (in this order).

This hierarchical test strategy protects the family-wise false positive error rate at the overall one-sided 0.025 level.

Key secondary endpoints 1., 2., and 3. will be analyzed as detailed in section 9.4.3.1.

Changes from baseline in each IDEEL modules scale score will be analyzed using an mixed model for repeated measures (MMRM). The analyses will include the fixed, categorical effects of treatment, visit (4 levels: Weeks

4, 8, 12, 16) and treatment by visit interaction. Subject will be considered as a random effect. The covariance matrix used will be "unstructured". Comparisons versus vehicle TID will be provided using least square means at each visit and overall. Missing data will be imputed according to the questionnaire manuals.

Changes from baseline in TFBUT and Fluorescein staining (NEI scale) will be analyzed by means of an ANCOVA model adjusting by pre-defined baseline factors (site, gender, age class, corresponding baseline value). Missing data will be imputed according to MI-RD (or wash-out approach, see section 9.4.3.1).

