10.2.2 Analysis details

Analysis of key secondary endpoints are detailed below in sections 10.2.2.1 - 10.2.2.6 and p-values to be evaluated for comparison between treatments in a sequential order are the following:

1. P-value of treatment variable from logistic regression model on proportion of patients reaching a value of Schirmer I test (without anesthesia) >10mm/5min at week 8 (section 10.2.2.1),
2. P-value of treatment variable from ANCOVA regression model on change from baseline in SANDE score for severity at week 12 (section 10.2.2.2),
3. P-value of treatment variable from ANCOVA regression model on change from baseline in SANDE score for frequency at week 12 (section 10.2.2.3),
- 4.1 P-value of treatment variable from MMRM regression model on IDEEL Quality of Life module at week 12 (section 10.2.2.4),
- 4.2 P-value of treatment variable from MMRM regression model on IDEEL Dry eye Treatment satisfaction & Bother module at week 12 (section 10.2.2.4),
- 4.3 P-value of treatment variable from MMRM regression model on IDEEL Dry eye Symptom bother module at week 12 (section 10.2.2.4),

- 4.4 P-value of treatment variable from MMRM regression model on IDEEL Quality of Life module at week 4 (section 10.2.2.4),
- 4.5 P-value of treatment variable from MMRM regression model on IDEEL Dry eye Treatment satisfaction & Bother module at week 4 (section 10.2.2.4),
- 4.6 P-value of treatment variable from MMRM regression model on IDEEL Dry eye Symptom bother module at week 4 (section 10.2.2.4),
- 5.1 P-value of treatment variable from MMRM regression model on Change from baseline in Cornea and conjunctiva vital staining with fluorescein NEI scale at week 4 (section 10.2.2.5),
- 5.2 P-value of treatment variable from MMRM regression model on Change from baseline in Cornea and conjunctiva vital staining with fluorescein NEI scale at week 8 (section 10.2.2.5),
- 5.3 P-value of treatment variable from MMRM regression model on Change from baseline in Cornea and conjunctiva vital staining with fluorescein NEI scale at week 12 (section 10.2.2.5),
- 6.1 P-value of treatment variable from MMRM regression model on Change from baseline in TFBUT values at week 4 (section 10.2.2.6),
- 6.2 P-value of treatment variable from MMRM regression model on Change from baseline in TFBUT values at week 8 (section 10.2.2.6),
- 6.3 P-value of treatment variable from MMRM regression model on Change from baseline in TFBUT values at week 12 (section 10.2.2.6).

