3. Each of the 200 imputed datasets will be analyzed using observed and imputed data. Rubin's rule will be used for combining results to draw inference.

If there are not enough retrieved dropouts for convergence of MI-RD regression model, a Copy Reference approach will be adopted to consider a MNAR mechanism for missing data. The final decision on the use of the MI-RD vs Copy-Reference for this endpoint will be done at the time of the analysis and reported in the CSR.

Whether for MI-RD or Copy-Reference approach, the adjusted estimated treatment differences in means for IDEEL module scores between cenegeimin and vehicle at each available timepoint will be displayed together with the corresponding two-side 95% confidence intervals and p-value.

10.2.2.5 Change from baseline in Cornea and conjunctiva vital staining with fluorescein NEI scale at week 4, week 8 and at week 12

Rules for derivation of NEI scores are reported in section 12.4. The change from baseline in Cornea and conjunctiva vital staining with fluorescein NEI scale will be analyzed by means of an MMRM adjusting by pre-defined factors (gender, age class, NEI scale baseline value, treatment, visit, and treatment by visit interaction; subject will be considered as a random effect). The covariance matrix used will be "unstructured". Comparisons versus vehicle TID will be provided using least square means at each visit and overall and a one-sided test will be used to test for differences between treatment groups.

For the imputation of missing data, a regression model will be created by including the baseline value, gender, age class, and intermediate scores up to week 12. Two hundred data sets will be generated, and the random seed number will be 240550. MI will be implemented in the following steps:

1. Partial imputation assuming MAR will be carried out to impute intermittent (non-monotone) missing data of NEI scale score based on a multivariate joint Gaussian imputation model using the MCMC method. A separate imputation model will be used for each treatment arm. In case of non-convergence or non-estimability issues, a single imputation model will be considered (with treatment arm added as explanatory variable to the model). A total of 200 datasets will be created. These datasets will be utilized in Step #2.

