12.3 IDEEL derivation

IDEEL is a 57-item questionnaire developed by Abetz et al. [3], that assess the impact of dry eye symptoms on everyday life. The possible range of each IDEEL score was 0 (complete disability) to 100 (no disability). This questionnaire consists of 3 modules:

- Dry eye Treatment satisfaction & Bother (10 questions) comprising two sections: “Treatment – In General” and “Treatment- Eye drops”.
- Dry eye Quality of Life (27 questions) comprising three sections: “Daily activities”, “Feelings” and “Work”.
- Dry eye Symptom Bother (20 questions).

Rules for the calculation of the IDEEL dimension scores are reported in Table 4 and Table 5.

Table 4: Calculation of IDEEL dimension scores

Parameter	Calculation
Item scaling	
 Dry Eye Treatment Satisfaction module: 
 Items 1-5 are scored on a 5-point Likert-like scale from 0 “none of the time” to 4 “all of the time” Items 6, 8-10 are scored on a 5-point Likert-like scale from 0 “all of the time” to 4 “none of the time” Item 7 is scored on a dichotomous scale: 1 “Yes”, 0 “No”. This item is not included in the calculation of the scores. Dry Eye Impact on Daily Life module: 
 Items 1-9 are scored on a 5-point Likert-like scale from 1 “all of the time” to 5 “none of the time”. Patients can also answer “I can no longer do this activity due to my dry eyes” (scored 0) or “I did not do this activity for reasons other than my dry eyes / Not applicable” (coded 6 but scored 5 for calculation of the scores) Items 10-21, 23-27 are scored on a 5-point Likert-like scale from 0 “all of the time” to 4 “none of the time” Item 22 is scored on a dichotomous scale: 1 “Yes”, 0 “No”. This item is not included in the calculation of the scores Dry Eye Symptom-Bother module: 
 Item 1 is scored on a 5-point Likert-like scale from 0 “none of the time” to 4 “all of the time” Items 2-20 are scored on a 4-point Likert-like scale from 1 “not at all” to 4 “very much”. Patients can also answer “I did not have this symptom / Not applicable” (scored 0).
Weighting of items	All items are given equal weight in the calculation of the scores.
Range of scores	0-100 scales.

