Scoring procedure	
 Dry Eye Treatment Satisfaction module: 
 Satisfaction with Treatment Effectiveness score: If patients never use treatment for their dry eyes (answer is 0 “none of the time” to item 1) then items 2-5 are missing, and the Satisfaction with Treatment Effectiveness score is missing. The Satisfaction with Treatment Effectiveness score is calculated if at least 50% (2 items) of the 4 items within the dimension are completed, non-missing; otherwise the score is set to missing. The Satisfaction with Treatment Effectiveness score is calculated as the mean of the non-missing item scores 2-5 multiplied by 25. Treatment-Related Bother score: If patients never use treatment for their dry eyes (answer is 0 “none of the time” to item 1) then item 6 is missing. If patients never use eye drops to treat their dry eyes (answer is 0 “No” to item 7) then items 8-10 are missing, and the Treatment-Related Bother score is missing. The Treatment-Related Bother score is calculated if at least 50% (2 items) of the 4 items within the dimension are completed, non-missing; otherwise the score is set to missing. The Treatment-Related Bother score is calculated as the mean of the non-missing item scores 6, 8-10 multiplied by 25. Dry Eye Impact on Daily Life module: 
 Impact on Daily Activities score: Response “I did not do this activity for reasons other than my dry eyes / Not applicable” for items 1-6 is re-coded 5 instead of 6. Other responses are scored with the original response code. The Impact on Daily Activities score is calculated if at least 50% (3 items) of the 6 items within the dimension are completed, non-missing; otherwise the score is set to missing. The Impact on Daily Activities score is calculated as the mean of the non-missing item scores 1-6 multiplied by 20. Emotional Impact score: The Emotional Impact score is calculated if at least 50% (6 items) of the 11 items within the dimension are completed, non-missing; otherwise, the score is set to missing. The Emotional Impact score is calculated as the mean of the non-missing item scores 10-20 multiplied by 25.

Parameter	Calculation

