Table 14.2.4.1	Schirmer I test (without anesthesia) >10mm/5min at week 8 - Logistic regression model - Multiple imputation	FAS		X
Table 14.2.4.2	Change from baseline in SANDE scores for severity at week 12. - Analysis of Covariance (ANCOVA) - Multiple imputation	FAS		X
Table 14.2.4.3	Change from baseline in SANDE scores for frequency at week 12. - Analysis of Covariance (ANCOVA) - Multiple imputation	FAS		X
Table 14.2.4.4.1.1	Change from baseline in IDEEL Quality of Life module (Daily activities) up to week 12 - MMRM - Multiple imputation	FAS		X
Table 14.2.4.4.1.2	Change from baseline in IDEEL Quality of Life module (Feelings) up to week 12 - MMRM - Multiple imputation	FAS		X
Table 14.2.4.4.1.3	Change from baseline in IDEEL Quality of Life module (Work) up to week 12 - MMRM - Multiple imputation	FAS		X
Table 14.2.4.4.2.1	Change from baseline in Dry eye Treatment satisfaction & Bother module (Treatment – In General) up to week 12 - MMRM - Multiple imputation	FAS		X
Table 14.2.4.4.2.1	Change from baseline in Dry eye Treatment satisfaction & Bother module (Treatment – Eye drops) up to week 12 - MMRM - Multiple imputation	FAS		X
Table 14.2.4.4.3	Change from baseline in IDEEL Dry eye Symptom bother module up to week 12 - MMRM - Multiple imputation	FAS		X
Table 14.2.4.5	Change from baseline in Cornea and conjunctiva vital staining with fluorescein NEI scale up to week 12 - MMRM - Multiple imputation	FAS		X
Table 14.2.4.6	Change from baseline in TFBUT up to week 12 - MMRM - Multiple imputation	FAS		X
Table 14.2.5.1	Absolute values and change from baseline in Schirmer I test at each timepoint.	FAS	X	X
Table 14.2.5.2.1	Absolute values and change from baseline in SANDE global scores at each timepoint.	FAS	X	X
Table 14.2.5.2.2	Absolute values and change from baseline in SANDE severity scores at each timepoint.	FAS	X	X
Table 14.2.5.2.3	Absolute values and change from baseline in SANDE frequency scores at each timepoint.	FAS	X	X
Table 14.2.5.3	Number of patients experienced a worsening in symptom scores (SANDE global score) and/or NEI score $\geq 50\%$ assessed at week 4	FAS		X

Number	Title	Population	KFR	Final Analysis
Table 14.2.5.4.1	Absolute values and change from baseline in IDEEL Quality of Life module at each timepoint.	FAS	X	X
Table 14.2.5.4.2	Absolute values and change from baseline in IDEEL Dry eye Treatment satisfaction & Bother module at each timepoint.	FAS	X	X

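### IDEEL steps 4.1, 4.2, 4.4 and 4.5 each need one module p-value, but the SAP defines only dimension scores, so these steps cannot be run as written and the 0.025 family-wise claim is not secured from step 4.1 onward

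*SAP*

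**What the plan says.** **The steps.** SAP 10.2.1 tests the key secondary endpoints in sequence at one-sided 0.025 and states that this protects the family-wise rate at that level. SAP 10.2.2 lists one p-value per step. Step 4.1 is the "P-value of treatment variable from MMRM regression model on IDEEL Quality of Life module at week 12 (section 10.2.2.4", and step 4.4 is the same module at week 4. Steps 4.2 and 4.5 do the same for Treatment satisfaction & Bother. SAP 10.2.2.4 also works at module level; it will report "the adjusted estimated treatment differences in means for IDEEL module scores".

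**The scores.** For their derivation 10.2.2.4 points to 12.3, where "Rules for the calculation of the IDEEL dimension scores are reported in Table 4 and Table 5". Those tables give three Quality of Life scores (items 1-6, 10-20 and 23-27) and two Treatment scores (items 2-5; items 6 and 8-10). Typical rules are "The Emotional Impact score is calculated as the mean of the non-missing item scores 10-20 multiplied by 25" and "The Treatment-Related Bother score is calculated as the mean of the non-missing item scores 6, 8-10 multiplied by 25". Only Symptom Bother has a single score.

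**The outputs.** SAP 15.1 splits the inferential tables in the same way, for example "Change from baseline in IDEEL Quality of Life module (Daily activities) up to week 12 - MMRM - Multiple imputation". The second Treatment table, "Dry eye Treatment satisfaction & Bother module (Treatment – Eye drops) up to week 12 - MMRM", carries the same number as the first. Both are labelled by questionnaire section and not by scored dimension.

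**The protocol.** Section 9.4.3.3 says "Changes from baseline in each IDEEL modules scale score will be analyzed using an mixed model for repeated measures (MMRM"). It gives neither a composite nor a pass rule.

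**Site.** SAP 6.1.1 stratifies randomisation by site. Protocol 9.4.3.3 adjusts the NEI and TFBUT ANCOVA for site. The MMRMs in SAP 10.2.2.5 and 10.2.2.6 have no site term. SAP 7.9 declares the use of MMRM but not the loss of site.

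**The concern.** A fixed sequence controls error because each step is one test named in advance. Here four steps name a quantity that has no formula. Whoever runs the analysis must choose between several p-values or invent a composite. Step 4.1 gates everything behind it, including the six NEI and TFBUT tests, so the choice reaches beyond the quality-of-life results.

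Timing adds to this. Under SAP 6.2, 7.9 and 15.1, the key first efficacy results follow lock and unblinding, precede the final analyses and include descriptive IDEEL tables. The IDEEL MMRM tables belong to the final analysis only. Unless the rule is fixed earlier, unblinded IDEEL comparisons could be seen before the decisive score is chosen.

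Three of the dimension scores are also missing by design for some patients. Table 4 sets the Work score to missing for patients not working, Satisfaction with Treatment Effectiveness to missing when item 1 says treatment is never used, and Treatment-Related Bother to missing when item 7 says no eye drops are used. SAP 10.2.2.4 imputes missing module scores without exempting these patients, while 7.8 refers IDEEL missing data to 12.3.

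A smaller matter is direction. A sentence in 12.3 says every IDEEL score runs up to 100 for no disability, but Table 4 coding and Table 5 make a higher Symptom Bother score worse. Steps 4.3 and 4.6 are one-sided, so the text should be consistent.

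**Working it through.** **1. The plan's own figure.** With one pre-specified p-value per step at 0.025, the first true null reached is rejected with probability at most 0.025. The SAP's 0.025 is reproduced, given one p-value per step.

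**2. Count of p-values.** Scores per visit: 3 + 2 + 1 = 6. Over weeks 12 and 4: 6 × 2 = 12 p-values for six listed steps.

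**3. Can a module score be inferred?** SAP 10.2.1 describes modules of 27 and 10 questions. Table 5 uses 6 + 11 + 5 = 22 and 4 + 4 = 8.
- Quality of Life items 7-9 and 21 are scaled in Table 4 but belong to no dimension; item 22 is a yes/no filter.
- Treatment items 1 and 7 are left out.
- Quality of Life items 1-9 run to 5 and the other scaled items to 4.

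No unique composite follows.

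**4. Step error by reading**, all dimensions of the module null:
- One composite, one named dimension or a fixed order: 2.5%.
- All must pass: at most 2.5% (at correlation 0.5, 0.16% for three scores and 0.46% for two).
- Any one suffices: 1 − P(all k statistics < 1.96). With independence, 1 − 0.975³ = 7.31% and 1 − 0.975² = 4.94%.

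| Assumed correlation | 0 | 0.5 | 0.7 | 0.9 |
|---|---|---|---|---|
| Any of three | 7.31% | 6.27% | 5.46% | 4.18% |
| Any of two | 4.94% | 4.54% | 4.17% | 3.52% |

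These are marginal values that ignore the earlier gates.

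**5. With the gates.** Gate powers are 95.8% and 94.0% (SAP 5) and an assumed 80% for each of steps 1-3.
- Independent: 0.958 × 0.940 × 0.8³ = 46.1% pass all five. Joint error is 0.461 × 7.31% = 3.37% (three scores) and 0.461 × 4.94% = 2.28% (two).
- Common correlation 0.5: 59.7% pass; joint error is 6.04% and 4.38%. Given that the gates passed, it is 6.04/59.7 = 10.1% and 4.38/59.7 = 7.3%.

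The two-score figures leave out step 4.1, which must also pass before 4.2. Under a global null the co-primary gate keeps the error at or below 2.5%.

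**6. Site.** Assume balanced sites, residual SD 1, site SD s and 80% power with site in the model (noncentrality 1.96 + 0.84 = 2.80). Without site, the standard error is overstated by √(1 + s²), so the effective critical value is 1.96 × √(1 + s²).
- s = 0.5: 1.96 × 1.118 = 2.19; error P(Z > 2.19) = 1.4%; power P(Z > 2.19 − 2.80) = 73%.
- s = 0.25: 1.96 × 1.031 = 2.02; error 2.2%; power 78%.

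Simulation of 10 sites with 10 patients each agrees: 1.5% error and 73.2% power without site at s = 0.5 (2.4% and 79.9% with it); 2.2% and 78.3% without site at s = 0.25.

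**The case against.** The strongest reply is that 10.2.2 lists exactly one p-value per step, 10.2.2.4 speaks of one module score and one module baseline value, and 15.1 has module-level descriptive tables. On that reading a single score was intended and only its formula is missing, which would keep 0.025. This stands as far as it goes: taken alone, the gap is mainly an undefined score. It does not close the gap, because the inferential tables are split by part and the protocol speaks of scale scores. SAP 7.8 cites a questionnaire manual for missing-data rules. Whether that manual defines module scores cannot be seen from the documents, and the SAP reproduces no such score.

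A reader might infer that the hierarchy runs at 7% or more. The documents do not support that. No passage states an any-dimension rule, and the correlations and the powers of steps 1-3 are assumptions. The independent two-score figure with gates (2.28%) shows no excess at all.

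A reader might also infer that dropping site undermines the NEI and TFBUT tests. It does not; the omission is conservative. The protocol's own IDEEL MMRM has no site term either, so the point is confined to NEI and TFBUT.

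**Conclusion.** The point holds as under-specification. Steps 4.1, 4.2, 4.4 and 4.5 cannot be run as written, and the unqualified 0.025 statement in SAP 10.2.1 is not secured from step 4.1 onward. The co-primaries and steps 1-3 each have one defined test and are unaffected. Steps 4.3 and 4.6 have a single score but sit behind the undefined gate, as do the NEI and TFBUT steps.

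The possible step error runs from at most 2.5% under any single-test or all-must-pass rule to 4.2-7.3% (three scores) or 3.5-4.9% (two) under an any-dimension rule. The upper ranges are marginal, rest on assumed correlations of 0.9 to 0, and bound the gap without showing that it is used.

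Two further defects are independent of that rule: scores that are missing by design would be imputed as ordinary missing data, and site leaves the NEI and TFBUT models undeclared. The site loss is about 7 points of power at a site SD of half the residual SD and about 2 at a quarter, with SDs and balance assumed.

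**What to change.** Before unblinding:

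1. **One test per step.** Choose a defined composite, one named Table 5 dimension, a fixed order of dimensions, or all-must-pass. Write it into 10.2.2 and 12.3 and declare it in 7.9. If a composite of the Table 5 dimensions is used, state that it covers 22 of 27 and 8 of 10 items, and how it is formed when one dimension does not apply.
2. **Tables.** Renumber and relabel the 15.1 MMRM tables to match the chosen scores.
3. **Structural missingness.** State that Work (not working), Satisfaction with Treatment Effectiveness (item 1: treatment never used) and Treatment-Related Bother (item 7: no eye drops) are not imputed as ordinary missing data. Take status at baseline so that the analysis does not select on a post-randomisation answer, and say how later changes are handled.
4. **Direction.** Correct the 12.3 sentence to agree with Table 5 for Symptom Bother.
5. **Site.** Add site to the NEI and TFBUT MMRMs, for example as the random effect used for the co-primaries, or list its removal in 7.9 with a reason.

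**Cost.** This is a SAP edit. At an assumed 80% power per score and correlation 0.5, an equal-weight composite has 93% (three scores) or 90% (two) power, falling to 21% or 37% if only one dimension responds. All-must-pass, or clearing a full ordered list, succeeds with 61% (three) or 69% (two); the 61% drops to 53% or 43% if 70% or 50% of patients work (assumed shares). Only that last pair allows for patients without a score, so the comparison somewhat favours the composite. Site adds one model term. The simulation had no repeated measures or imputation, so convergence with the unstructured covariance should be checked.
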